If the subject is considered mentally competent to provide consent, the subject will be informed and asked for consent. However, if the subject lacks decision-making capacity, the investigator will search for a legal representative available. Every 24 hours, the investigator will assess whether the subject or the legal representative is capable of making a decision about participation in this trial in the current situation. If not, every 24 hours later will be evaluated if informed consent can be obtained. If there is no legal representative available, study procedures will be continued until a proxy is present.

The subject and/or his/her legal representative will be given sufficient time to read the ICF and the opportunity to ask questions. However, this time period is limited to the duration of the hospital admission. After this explanation, consent should be appropriately recorded by means of the subject's or the legal representative's personally dated signature and authorised study staff's personally dated signature. After obtaining the consent, a copy of the ICF must be given to the subject.

Copies or a second original of the signed ICF will be given to the subject and the original will be maintained with the subject's records. If new safety information results in significant changes in the risk/benefit assessment, the ICF should be reviewed and updated if necessary. All subjects for whom this is relevant should be informed of the new information and give their consent to continue the study.

If a patient who has been enrolled into the study refuses to participate and sign the ICF, or if his/her legal representative refuses this in case of the patient's incapacity, participation into the study will be terminated immediately. Data from non-consenting subjects will only be used when there is no written objection from the subject or representative. In an effort to describe the non-consenting population we will ask the subject or his/her representative to allow the use of routinely collected data in a coded manner. The refusal and the reason, if available, will be recorded in the patient's clinical chart.

If a patient has died before deferred consent has been obtained, his/her representative will be informed about the study treatment the patient may have received, trial procedures and use of the collected data. A separate information letter will be sent to a representative of the patient.

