**Main objective**

The aim of the current study is to increase knowledge about the deferred consent procedure in acute stroke research. We will collect and analyse data on logistics of the procedure and on patient recall, satisfaction, and comprehension at three months from randomization.

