**Specific objectives**

1. To estimate the proportions of patients and proxies that give consent for and object against enrolment in acute stroke trials using deferred consent procedures;
2. To map the workflow and timeline of the deferred consent procedure;
3. To explore the personal feeling of capability of patients and proxies to provide consent for participation in an acute stroke controlled trial;
4. To explore appreciation of patients and proxies of the deferred informed consent procedure;
5. To investigate recall and comprehension by patients and proxies of study methods of the acute stroke trial for which they provided deferred consent;
6. To compare the observations on 1-5 with data from previous acute stroke trials.

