### Duration of data collection

We aim to collect data on deferred consent of 300 patients during the first year of enrolment in the CONTRAST trials. Data collection will start 3 months after the first inclusion in the study.

**Patient recruitment**Patients / proxies who provided consent for participation in the trial

During the 3 month telephone follow-up of the CONTRAST trial, the subject who provided consent will be asked to participate in this substudy. The purpose of the study will be explained and the study procedures will be described. Questionnaire 1 will be sent to their home address. The feeling of capability for giving consent, appreciation of the informed consent process and recall and comprehension will be explored in this questionnaire. For participation in this substudy, no additional written informed consent from individual subjects is needed.

Patients / proxies who withheld consent for participation in the trial

The patient or proxy who refused to give deferred consent for participation in the CONTRAST trial will be approached. The purpose of the study will be explained and the study procedures will be described. They will be asked to only fill out Questionnaire 2, which concerns the reasons for not giving consent. It will be emphasized that it is not mandatory to answer. No additional questionnaires or interviews will be carried out within this patient group.

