**Questionnaire 1 – patient – after 3 months**

Enquêtevragen als patiënt toestemming heeft gegeven voor deelname aan het onderzoek.  
[voor start vragenlijst: informatie deferred consent en redenen voor dit onderzoek]

Algemeen

Wat is uw hoogst genoten opleiding? (keuze)

- geen
  
- basisschool
  
- lager beroepsonderwijs (LBO, VMBO)
  
- middelbaar algemeen voorbereidend onderwijs (MAVO)
  
- middelbaar beroepsonderwijs (MBO)
  
- hoger algemeen voorbereidend, wetenschappelijk onderwijs (HAVO, VWO)
  
- hoger beroepsonderwijs (HBO)
  
- kandidaats/propedeuse wetenschappelijk onderwijs (WO)
  
- (post) wetenschappelijk onderwijs
  
- weet niet / wil ik niet zeggen

Vragen over uw kennis en begrip over de methode van het onderzoek

1. Vindt u zelf dat u voldoende weet over het onderzoek?

I. Ik vind dat ik voldoende weet over het **doel** van het onderzoek

- Ja
  
- Nee

II. Ik vind dat ik voldoende weet over de **opzet** van het onderzoek

- Ja
  
- Nee

2. Heeft u de informatiebrief gelezen?

- Ja
  
- Nee

3. Heeft u de informatiebrief begrepen?

- Ja
- Nee

4. Welke behandeling werd in dit onderzoek getest? (vrije tekst)

5. Hoe werd besloten welke behandeling u kreeg? (vrije tekst)

6. Welke behandeling heeft u of uw naaste gekregen? (vrije tekst)

7. Waren er risico's en nadelen verbonden aan meedoen aan het onderzoek? (ja/nee + vrije tekst)

8. Waren er voordelen verbonden aan meedoen aan het onderzoek? (ja/nee + vrije tekst)

9. Was deelname aan het onderzoek vrijwillig of verplicht?

- Vrijwillig
- Verplicht

10. Was het mogelijk uw toestemming voor deelname aan het onderzoek in te trekken?

- Ja
- Nee

11. Wie had toegang tot uw persoonlijke gegevens en ziektegeschiedenis? (vrije tekst)

Vragen over uw waardering over de toestemmingsprocedure

12. Voelde u zich destijds in staat om te beslissen over deelname aan dit onderzoek?

- Ja (ga naar vraag 16)
- Nee (ga hieronder verder)

13. Wie had u liever deze beslissing willen laten maken?

- Mijn behandelend arts
- Een familielid, namelijk: .....
- Toestemming voor dit onderzoek vind ik niet nodig

14. Waarom voelde u zich niet in staat om te beslissen over deelname aan dit onderzoek?  
(meerdere antwoorden mogelijk)

- I. Ik vond het te veel informatie
- II. Ik begreep de uitleg niet goed
- III. Ik voelde mij gestresst
- IV. Deze vraag kwam te snel na de beroerte
- V. Ik heb te weinig bedenktijd gehad
- VI. Anders, namelijk: .....

15. Had u genoeg tijd om een beslissing te maken?

- Ja
- Nee

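### Recall of trial methods is measured only by a posted questionnaire that does not record use of the information letter or help, so recall cannot be separated from looking up

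*Protocol*

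**What the plan says.** Recall at three months is a stated aim at three levels. Section 2 lists it under the tertiary objectives. Appendix 12, Main objective, says: "We will collect and analyse data on logistics of the procedure and on patient recall, satisfaction, and comprehension at three months from randomization". Specific objective 5 reads: "To investigate recall and comprehension by patients and proxies of study methods of the acute stroke trial for which they provided deferred consent".

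The instrument is Questionnaire 1. Under Duration of data collection, in the part on patient recruitment, the protocol says "Questionnaire 1 will be sent to their home address" and "The feeling of capability for giving consent, appreciation of the informed consent process and recall and comprehension will be explored in this questionnaire". The procedure for objective 5 refers back to objective 3, which is the same posted form. No other measurement of recall is described.

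The patient and proxy versions share the same opening items:

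- Item 1 asks whether respondents feel they know enough about the aim and set-up of the research.
- Items 2 and 3 ask whether the information letter was read and understood; item 2 begins "Heeft u de informatiebrief gelezen".
- Items 4 to 11 ask for facts: treatment tested, how allocation was decided, treatment received, risks, benefits, voluntariness, the right to withdraw, and who had access to personal data.

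A placeholder above the form announces introductory text, "voor start vragenlijst: informatie deferred consent en redenen voor dit onderzoek", that is, information on deferred consent and the reasons for the research. On consent papers, section 11.2 states: "After obtaining the consent, a copy of the ICF must be given to the subject".

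**The concern.** Items 4 to 11 are completed at home, unsupervised, by people who were given written trial information about three months earlier, and they follow two questions that name that information. The form as shown does not ask respondents to answer from memory, and it does not record whether they looked anything up, had help, or filled in the form themselves. A high proportion correct could mean good recall, a letter at hand, or a helpful relative.

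This matters for two reasons. Appendix 12, Handling of data and documents, says results will be reported during active enrolment and may affect the consent procedures of the trials, so a recall figure that flatters deferred consent could be acted on. And because the information is never collected, no later analysis can recover it.

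**Working it through.** **What the text establishes.** The protocol has no sample-size or precision figure for recall, so there is no stated calculation to reproduce. The passages, set side by side, give:

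1. Recall at three months is an objective (section 2; Appendix 12, Main objective and Specific objectives).
2. Its only measure is a posted form (Duration of data collection; procedures for objectives 3 and 5).
3. The facts asked for in items 4 to 11 largely match what section 11.2 requires to be explained at consent: aims, methods, benefits, hazards, voluntariness, withdrawal and access to records. The letter is therefore a likely source of answers, although its text is not at hand. Item 6, on the treatment received, is individual; nothing says the letter gives the allocation, so help there would come from another person.
4. No item records consultation, help or who completed the form. Section 8.3.11 foresees completion by a representative for the EQ-5D-5L; Questionnaire 1 has patient and proxy versions but does not ask who filled it in.

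**Direction.** Looking up mostly turns a wrong or blank answer into a correct one, so any bias in the factual items is likely upward.

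**Size, as illustration only.** Let p be true unaided recall of an item and q the share of non-recallers who look the answer up and get it right. Neither is in the protocol.

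Observed share = p + q(1 − p), so bias = q(1 − p).

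| True recall p | q = 0 | q = 10% | q = 25% | q = 50% | 95% half-width, n = 300 |
|---|---|---|---|---|---|
| 30% | 30% | 37% | 47.5% | 65% | 5.2 points |
| 50% | 50% | 55% | 62.5% | 75% | 5.7 points |
| 70% | 70% | 73% | 77.5% | 85% | 5.2 points |

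Half-width = 1.96 × √(p(1 − p)/n). Bias equals the half-width when q = half-width/(1 − p): 0.052/0.70 = 7%, 0.057/0.50 = 11%, 0.052/0.30 = 17%.

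**Denominator.** The 300 in Appendix 12 is a target number of patients across the CONTRAST trials, not of returned forms. Those who refuse consent receive only Questionnaire 2, proxies of deceased patients are not interviewed, and some forms will not come back. With an assumed 200 or 150 returns and p = 0.5, the half-width is 1.96 × √(0.25/200) = 6.9 or 1.96 × √(0.25/150) = 8.0 points. Bias does not shrink as n grows, but against these half-widths a small look-up share matters less.

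**Would analysing only non-consulters solve it?** Take p = 60%, half of non-recallers looking up, and 95% of look-ups correct.

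- All respondents: 0.60 + 0.20 × 0.95 = 79%.
- Non-consulters only: 0.60/(0.60 + 0.20) = 75%, still 15 points too high, because the restriction removes people who did not remember.
- If instead half of all respondents consult, regardless of memory, all respondents give 0.5 × 0.60 + 0.5 × 0.95 = 77.5%, and non-consulters give the true 60%.

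The data cannot show which pattern applies, so the restricted figure cannot be the main result.

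**The case against.** Much can be said for the plan.

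- **Posting is defensible.** The three-month call is made by a blinded assessor, and item 6 asks which treatment was received. Keeping these items out of that call protects the primary outcome. This stands, and the fix respects it.
- **Recall is not the only construct.** Objective 5 also covers comprehension, and the patient form heads this part as knowledge and understanding. Looking up undermines the recall claim more than the comprehension claim, and hardly touches the opinion items from 12 onward. This stands.
- **The trial may not be explained again beforehand.** A reader might infer from the preamble, and from the explanation given at recruitment, that respondents are told the answers first. The documents do not support that. At recruitment the explanation follows the invitation to the substudy, and the same placeholder heads Questionnaire 2 for people who refused consent. The wording is ambiguous, since item 4 uses the same Dutch term for the trial, but nothing shows that answers are supplied. The introductory text is not reproduced, so it might contain an instruction to answer from memory; an instruction would still not record what respondents did.
- **Possession of the form is inferred.** Section 11.2 has the copy given to the subject at consent. That it is at hand three months later is not stated, and is less certain for proxies. That items 2 and 3 prompt people to fetch the letter is conjecture.
- **Comparisons are less exposed than they seem.** Objective 6 says "To compare the observations on 1-5 with data from previous acute stroke trials", which nominally includes recall. But the comparison specified under the workflow section and Statistical analysis concerns consent numbers, consent parameters and time intervals, which looking up cannot affect. No comparison of recall by education or between patients and proxies is specified.

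None of this removes the central gap: if respondents consult the letter or another person, the data will not show it.

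**Conclusion.** The point holds as a minor design weakness of a descriptive substudy. Followed as written, the plan cannot separate recall from looking up, and the recall proportion may be too high by an unknown amount. Under assumed look-up by 10% of non-recallers the shift is 3 to 7 points for true recall of 70% to 30%; with no look-up it is zero. Everything beyond the direction of the bias rests on assumed rates.

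A reader might go further and conclude that the recall result is inflated and does not measure memory. The documents do not support that: they give no look-up rate and do not show that the form or letter is used at completion. The supported statement is that correct answers may reflect assisted recall. Randomisation, safety monitoring and the primary outcome are untouched.

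**What to change.** 1. Place items 4 to 11 before items 2 and 3, and before any introductory text that could cue answers, in both the patient and proxy versions.
2. Add an instruction to answer these items from memory, without the letter and without help.
3. Add one item asking whether the letter or another person was consulted while answering, and who completed the form.
4. Report recall for all respondents as the main result, with results by reported consultation alongside as a sensitivity analysis. Do not make non-consulters the main result, because that restriction is itself selective. Describe the measure as possibly assisted recall.

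Reordering does not stop a respondent from reading ahead on paper, and reported consultation may be incomplete, so the caveat in step 4 remains. A separate telephone call by someone other than the blinded outcome interviewer would control this better, but needs extra staff and is not required.

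The cost is slightly more questionnaire text and a recall figure that may be lower. The change has to be made before forms are sent, since the missing information cannot be added afterwards.

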## Study procedures

### Baseline information

The following baseline characteristics, already collected in the CONTRAST trials, will be used: age, sex, baseline NIHSS - including NIHSS subitems, stroke type, study site and treatment arm (intervention vs. control). The 3 month modified Rankin Scale score (mRS) will also be used.

Additionally we will document the educational level of the subject who provided consent.

### 1. Patient enrolment

The CONTRAST trials use different deferred informed consent forms (ICFs):

- 1) Patient: the patient is mentally competent to provide consent, as estimated by the researcher/clinician
  
- 2) Proxy (partner or family member): the patient is not mentally competent to provide consent, as estimated by the researcher/clinician, and the researcher/clinician believes it is ethically valid to inform and ask for consent

In case the patient has deceased before consent could be asked, the data which has been documented so far may be used in an anonymous fashion for study purposes and the proxy will be informed (figure 1).

The following data will be documented regarding patient enrolment:

- the number of patients providing consent vs. not providing consent + reasons for not providing consent
  
- the number of proxies providing consent vs. not providing consent + reasons for not providing consent
  
- the number of patients who deceased before consent could be asked
  
- the number of patients that withdrew their consent within 3 months

## 2. Deferred consent workflow and timeline

The study protocols of the CONTRAST trials state that deferred informed consent will be obtained within the first 24 hours after enrolment. In the MR ASAP trial, the nitroglycerin patch will be removed after 24 hours. However, when a patient refuses to provide consent, the patch will be removed directly. For the subsequent CONTRAST trials, the first follow-up CT scan will be performed 24 hours after randomisation (Figure 1).

We will document time intervals from symptom onset until consent has been obtained. The timeline will contain the following time measurements, if applicable.

1. MR ASAP: onset – randomisation/treatment – ER – inclusion in subsequent CONTRAST trial – IVT – IAT – start IC conversation – signature patient/proxy
2. MR CLEAN-NO IV: onset – inclusion in MR ASAP – ER – randomisation – IVT – IAT – start IC conversation – signature patient/proxy
3. MRCLEAN-MED: onset – inclusion in MR ASAP – ER – IVT – randomisation – IAT – start IC conversation – signature patient/proxy
4. MRCLEAN-LATE: onset – inclusion in MR ASAP – ER – IVT – randomisation – IAT – start IC conversation –signature patient/proxy

*ER: emergency room; IVT: intravenous thrombolysis; IAT: intra-arterial treatment; IC: informed consent*

On the ICF we will record date and time of:

- start of informed consent conversation; and
- signature of patient or proxy.

The remaining time measurements will be recorded in the electronic case report form (eCRF).

We will compare of the numbers and time intervals of patient vs. proxy consent in our study with data from the Multicenter Randomized CLinical trial of Endovascular treatment for Acute Ischemic stroke in the Netherlands (MR CLEAN).

**3. Capability of patients and proxies of providing consent for participation**

After 3 months the primary outcome of the CONTRAST trials will be assessed during a telephone interview by a blinded assessor. During the follow-up interview the patient or proxy will be asked if they would like to continue participating in this substudy. Questionnaire 1 will be sent to their home address with the questions regarding this objective and objective 4 and 5.

**4. Appreciation of patients and proxies of the deferred informed consent procedure**

See objective 3.

**5. Recall and comprehension of study methods of the trial**

See objective 3.

**Statistical analysis**

Results will be reported for the trials separately and the CONTRAST trials all together. This is an observational study. We will describe the distribution of consent process variables, as well as time and logistics parameters. We will relate characteristics of the neurological deficit, as measured with the NIHSS scale with the legal capability status of the patient. Finally, we will compare the consent parameters, including time intervals, with data from the Multicenter Randomized Clinical Trial of Endovascular Treatment for Acute Ischemic Stroke in the Netherlands (MR CLEAN). Variables will be compared with Chi square test for categorical variables and Mann-Whitney for continuous variables. A p-value below 0.05 will be considered statistically significant.

**Ethical considerations**

This study will be performed according to ICH-GCP principles, the Declaration of Helsinki as most recently amended in 2013, and national regulatory requirements, as the European trial Directive and the European privacy regulation. We are awaiting approval by the institutional review board of the Erasmus MC University Medical Center.

**Nature and extent of the burden of participation**

The study procedures will require an estimated maximum of 30 minutes of the subject's time at 3 months (Questionnaire 1) and 5 minutes of the subject's time during hospital admission (Questionnaire 2) and. We therefore consider the burden minimal.

[figure not shown]
**Handling of data and documents**

The results of this substudy will be reported during the active enrolment in the CONTRAST trials. The conclusions of this substudy may have consequences for the actual consent study procedures.

**Questionnaire 1 – patient – after 3 months**

Enquêtevragen als patiënt toestemming heeft gegeven voor deelname aan het onderzoek.  
[voor start vragenlijst: informatie deferred consent en redenen voor dit onderzoek]

Algemeen

Wat is uw hoogst genoten opleiding? (keuze)

- geen
  
- basisschool
  
- lager beroepsonderwijs (LBO, VMBO)
  
- middelbaar algemeen voorbereidend onderwijs (MAVO)
  
- middelbaar beroepsonderwijs (MBO)
  
- hoger algemeen voorbereidend, wetenschappelijk onderwijs (HAVO, VWO)
  
- hoger beroepsonderwijs (HBO)
  
- kandidaats/propedeuse wetenschappelijk onderwijs (WO)
  
- (post) wetenschappelijk onderwijs
  
- weet niet / wil ik niet zeggen

Vragen over uw kennis en begrip over de methode van het onderzoek

1. Vindt u zelf dat u voldoende weet over het onderzoek?

I. Ik vind dat ik voldoende weet over het **doel** van het onderzoek

- Ja
  
- Nee

II. Ik vind dat ik voldoende weet over de **opzet** van het onderzoek

- Ja
  
- Nee

2. Heeft u de informatiebrief gelezen?

- Ja
  
- Nee

3. Heeft u de informatiebrief begrepen?

- Ja
- Nee

4. Welke behandeling werd in dit onderzoek getest? (vrije tekst)

5. Hoe werd besloten welke behandeling u kreeg? (vrije tekst)

6. Welke behandeling heeft u of uw naaste gekregen? (vrije tekst)

7. Waren er risico's en nadelen verbonden aan meedoen aan het onderzoek? (ja/nee + vrije tekst)

8. Waren er voordelen verbonden aan meedoen aan het onderzoek? (ja/nee + vrije tekst)

9. Was deelname aan het onderzoek vrijwillig of verplicht?

- Vrijwillig
- Verplicht

10. Was het mogelijk uw toestemming voor deelname aan het onderzoek in te trekken?

- Ja
- Nee

11. Wie had toegang tot uw persoonlijke gegevens en ziektegeschiedenis? (vrije tekst)

Vragen over uw waardering over de toestemmingsprocedure

12. Voelde u zich destijds in staat om te beslissen over deelname aan dit onderzoek?

- Ja (ga naar vraag 16)
- Nee (ga hieronder verder)

13. Wie had u liever deze beslissing willen laten maken?

- Mijn behandelend arts
- Een familielid, namelijk: .....
- Toestemming voor dit onderzoek vind ik niet nodig

14. Waarom voelde u zich niet in staat om te beslissen over deelname aan dit onderzoek?  
(meerdere antwoorden mogelijk)

- I. Ik vond het te veel informatie
- II. Ik begreep de uitleg niet goed
- III. Ik voelde mij gestresst
- IV. Deze vraag kwam te snel na de beroerte
- V. Ik heb te weinig bedenktijd gehad
- VI. Anders, namelijk: .....

15. Had u genoeg tijd om een beslissing te maken?

- Ja
- Nee

16. Had u liever gewild dat de vraag voor deelname aan het onderzoek op een ander moment was gekomen?

- Ja (ga naar de volgende vraag)
- Nee (ga naar vraag 19)

17. Zo **ja**, op welk moment had u liever gewild dat deze vraag aan u was gesteld? (één keuze)

- Eerder: nog vóór alle studiehandelingen, inclusief de behandeling
- Eerder na de studiehandelingen: binnen 12 uur in plaats van binnen 24 uur
- Later: binnen 72 uur in plaats van binnen 24 uur

18. Had u het goed vonden als een familielid voor u deze beslissing had gemaakt?

- Ja
- Nee

19. Welke beslissing zou uw familielid hebben gemaakt, als uw familielid voor u deze beslissing had gemaakt?

[figure not shown]
- Meedoen met het onderzoek

- Niet meedoen met het onderzoek

20. Als de toestemmingsprocedure op een later tijdstip had plaatsgevonden (bijvoorbeeld binnen 72 uur in plaats van binnen 24 uur), zou u ermee akkoord gaan als er dan ook meer studiehandelingen (zoals bloedprikken of een CT-scan van het hoofd) zouden zijn uitgevoerd?

- Ja
- Nee

21. Hoe ervaart u de uitgestelde toestemmingsprocedure? (onderstaande Likert schaal + vrije tekst)

